Metformin in Heart Failure (Met-HeFT)

[name] MD PhD, March 3rd 2020

Protocol Version 10

Main Study: IRB AAAR5389 (CUIMC)

PET Sub-study: IRB AAAR9360 (CUIMC)

HAZMAT (JRSC): APH-AAA26251

NCT 03331861

Summary of Protocol Changes from v.9

- We are modifying any hospitalization within the past 3 months as an exclusion criteria to any heart failure hospitalization within the past 3 months.**
- We are adding a stationary bicycle as a mode for performing a cardiopulmonary exercise test for patients who cannot or do not want to exercise on a treadmill.**

Summary of Protocol Changes from v.8

- Liver Function Tests were reclassified as a screening test from a baseline test since abnormal liver function is an exclusion criteria and not an outcome.
- Listing venous lactate as a baseline laboratory value to reflect Table 1 procedural timeline more accurately
- Specific statement that any laboratory value obtained for clinical purposes within three months of screening can be used for screening
- Removal of [name] from the DSMB and replacement with [name]

Summary of Protocol Changes from v.7

- Microbiome elements were removed from the protocol

Summary of Protocol Changes from v.6

- The PET radiotracers oxygen, palmitate and acetate are not available.
- The PET protocol is changed to just FDG and NH3, both of which are FDA approved.
- Change in effective radiation dose due to change in radiotracers
- We are pre-specifying a plan to pursue IRB/RDRC/JRSC approval for palmitate, acetate and oxygen when available from research radio-pharmacy to be started during active enrollment of the Met-HeFT trial.

Purpose:

This study evaluated the efficacy of metformin on myocardial function in non-diabetic patients with systolic heart failure. Fifty patients will be randomized to either metformin or placebo for 6 months in addition to regular therapy.

Hypothesis

The primary hypothesis is that metformin will improve myocardial performance in patients with

stable systolic heart failure without diabetes.

Endpoints

Primary endpoint: change in VE/VCO₂ over 6 months of treatment.

Secondary endpoints:

- a) heart failure decompensation (unscheduled office IV diuretic therapy, ED visit for decompensated heart failure or hospital admission for decompensated heart failure)
- b) Minnesota Health Living with Heart Failure Questionnaire Score
- c) LVEF,
- d) GLS and GCSR
- e) BNP
- f) body weight
- g) changes in dyspnea assessment score (VAS and 7-Likert scale),

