The primary outcome in this study will be change in VE/VCO₂ slope. The VO₂ change outcomes will be assessed for normality using standard visual assessments (Q-Q plots and histograms) and statistical tests (Kolmogorov-Smirnov). If VE/VCO₂ slope change demonstrates evidence for non-normality, we will natural log transform values for our primary analyses. Prior to testing for differences, we will compare important clinical, laboratory and demographic characteristics between groups (treatment vs. control) to ensure that randomization achieved between groups balance on these important covariates. For variables that are unbalanced by treatment group (determined via statistically significant difference $p<0.05$), we will include these variables in multivariable models of the primary endpoint as described below. Linear regression models will be used to regress mean weight change on treatment group using intention-to-treat principles. If preliminary descriptive analyses indicate a need for multivariable models (see above), the relevant adjustments will be made to our regression models. Analysis of secondary outcomes will be conducted using contingency tables and Fisher's exact chi-square tests; for these outcomes, we will also utilize a modified Poisson regression model with robust error variance to assess the relative risk (separate regressions for each outcome). This modified Poisson model has been described previously and allows for multivariable models to be constructed should they be deemed necessary. Once a patient is randomized, they will be included in final analyses according to intention-to-treat principles regardless of whether they complete the study protocol. If patients are lost-to-follow up and final outcome assessments cannot be made we will use the "last observation carried forward" approach to assign a final outcome value. Additional sensitivity analyses will be performed by assigning final outcome values assuming patients in the treatment group had 10% lower mean weight loss and patients in the control group had 10% greater mean weight loss. This is very conservative approach that will inform the potential for differential outcomes according to follow-up status to explain our observed findings. However, we expect very little loss-to-follow up as these patients receive regular care at our center and are likely to return to the hospital regardless of continued study participation.

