Power for VE/VCO₂: We base the sample size calculation on data from Wong et al (31). We estimate the average effect size of metformin on the slope of VE/VCO₂ to be -5 with a starting average slope of 32 and a variance of 6. In order to achieve 83% power with an alpha of 0.05, we will enroll 25 patients in each arm.

Positron Emission Tomography (PET) Sub-study (IRB AAAR 9360)

The goal of this sub-study is to enroll patients to undergo cardiac PET imaging before and after treatment with either metformin or placebo. In this pilot sub-study, we will recruit patients at the time of their enrollment into Met-HeFT to undergo serial PET scans with metabolic tracers. We will specifically use FDA approved radiotracers for this study including ¹⁸F-Fluorodeoxyglucose (¹⁸F-FDG) to track myocardial glucose consumption and ¹³N-ammonia (¹³N-NH₃) to track perfusion. With these combination of radiotracers, we will be able to quantitatively measure myocardial metabolism and its reliance on different pathways that may be influenced by metformin.

Consecutive patients in Met-HeFT will be recruited at the time they are enrolled in the trial to be included in the sub-study. The decision to enroll in this sub-study will have no effect on their enrollment in Met-HeFT. After enrollment, patients will undergo a PET scan using two radiotracers: ¹⁸F-FDG and ¹³N-ammonia. Scans will occur prior to initiation of the study drug and at the 6 month end of study mark. Patient randomization will be maintained and both the study participants, coordinators and investigators will be blinded to patient assignment.

Inclusion/Exclusion Criteria: Any patient enrolled and meeting all inclusion criteria for Met-HeFT will be eligible to elect for inclusion into this sub-study.

Pregnancy Test: Women of childbearing potential will provide a urine specimen to determine if they are pregnant. Pregnant women will be excluded from the study. The source of the urine specimen will be from Columbia and/or NYPH Subjects/Patients or repositories managed by Columbia. The specimen will be labeled with direct identifiers.

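### The stated 83% power does not follow from a variance of 6; it fits an SD of 6, and the plan does not say whether the 6 is the spread at one visit or of the 6-month change

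*Combined protocol and SAP*

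**What the plan says.** The paragraph headed Power for VE/VCO₂ is the only sample-size justification in the protocol. It reads "We base the sample size calculation on data from" a cited publication (reference 31). The assumed effect of metformin is put at minus "5 with a starting average slope of 32 and a variance of 6". From these inputs the paragraph draws its conclusion on size and power: "In order to achieve 83% power with an alpha of 0.05, we will enroll 25 patients in each arm".

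The endpoint being powered is a change. The Endpoints section has "Primary endpoint: change in VE/VCO₂ over 6 months of treatment", and the Statistical Approach has "The primary outcome in this study will be change in VE/VCO₂ slope".

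The protocol gives no SD of the change, no correlation between the baseline and final slope, and no statement of whether alpha is one- or two-sided. The Statistical Approach adds covariates to the regression only when they differ between arms at p<0.05, so adjustment for the baseline slope is not planned as such.

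**The concern.** There are two separate difficulties.

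1. The printed inputs and the printed result disagree by a wide margin. Taken literally, a variance of 6 calls for 5 to 6 patients per arm if it refers to the change. If it refers to one visit and the visits are uncorrelated, it calls for 9 to 10. The plan enrols 25. A reader has to guess that one word is wrong before the calculation can be reproduced.
2. Replacing the word does not settle the matter. The 6 stands directly after "a starting average slope of 32", so it can be taken as the spread of the slope at baseline. A comparison of 6-month changes needs the spread of the change. The two are equal only when the correlation between visits is 0.5.

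At stake is whether the stated power applies to the primary endpoint, and whether anyone can verify it from the protocol.

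**Working it through.** **Inputs from the protocol.** Difference d = 5 in absolute value; n = 25 per arm, allocated 1:1; alpha 0.05; stated power 83%; spread 6, called a variance. The starting slope of 32 plays no part in a two-sample comparison of changes. Two-sided alpha is an assumption, tested below.

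**Formulas.** For SD s of the outcome analysed:

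- Normal approximation: power = Φ( d / (s·√(2/n)) − 1.960 ).
- Patients per arm for 83% power: n = 2·s²·(1.960 + 0.954)² / d², rounded up.
- The t-test figures use the noncentral t distribution with 2n − 2 degrees of freedom (48 for 25 per arm).

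**Trying to reproduce 83%.**

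*Variance 6, of the change.* s = √6 = 2.449. The standard error is 2.449 × √(2/25) = 0.693, and 5/0.693 = 7.22. Power is above 99.99% by either method. For 83%, n = 2 × 6 × 8.492 / 25 = 4.08, so 5 per arm. By t-test, 5 per arm gives 80.6% and 6 per arm gives 88.9%, so 6 are needed.

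*Variance 6, at one visit, correlation 0.* The variance of the change is 2 × 6 = 12, so s = 3.464 and 5/(3.464 × √(2/25)) = 5.10. Power is 99.9% by either method. For 83%, n = 2 × 12 × 8.492 / 25 = 8.15, so 9 per arm. By t-test, 9 per arm gives 82.0% and 10 per arm gives 86.2%, so 10 are needed. Any positive correlation raises power further.

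*SD 6, of the change.* The standard error is 6 × √(2/25) = 1.697, 5/1.697 = 2.946, and Φ(2.946 − 1.960) = 83.8%. The t-test gives 82.3%. For 83%, n = 2 × 36 × 8.492 / 25 = 24.46, so 25 per arm. By t-test, 26 are needed (83.8%).

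| Reading of the 6 (25 per arm, two-sided) | Power, t-test | Power, normal | Per arm for 83%, normal / t-test |
|---|---|---|---|
| Variance of the change | >99.99% | >99.99% | 5 / 6 |
| Variance at one visit, correlation 0 | 99.9% | 99.9% | 9 / 10 |
| SD of the change | 82.3% | 83.8% | 25 / 26 |

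**Working backwards.** The SD that gives exactly 83% with 25 per arm is 5.94 (t-test) or 6.07 (normal), that is, a variance of 35.3 or 36.8, close to 6² = 36.

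**Sidedness.** With an SD of 6 and a one-sided alpha of 0.05, power is about 90% (89.6% by t-test, 90.3% by normal approximation). The stated 83% therefore matches a two-sided test.

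**If 6 is the SD at one visit.** Assuming equal SDs at both visits and correlation r, the SD of the change is 6·√(2(1 − r)). The protocol gives no r; the values below are assumptions.

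| Assumed r | SD of change | Power, t-test |
|---|---|---|
| 0.3 | 7.10 | 68% |
| 0.5 | 6.00 | 82% |
| 0.7 | 4.65 | 96% |

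Power equals 83% at r = 0.49 (normal) or 0.51 (t-test).

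**The case against.** The strongest reply is that one word is wrong and everything else fits. Read the 6 as an SD, test two-sided, and the standard formula returns the planned 25 per arm. No patient number, endpoint or analysis changes through the mislabel. That stands, and it limits the weight of the point. It does not make the paragraph correct as printed, and it leaves the second question open. A planner who entered a single-visit SD into the same formula would have obtained the same 83%, so the match cannot show which SD was used.

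A second reply is that the correlations above come from outside the protocol and apply only to an unadjusted analysis of change. Both parts are true. If 6 is a single-visit SD and the baseline slope were a covariate, the residual SD would be 6·√(1 − r²), and t-test power would be 82%, 86%, 92% and 98% at r = 0, 0.3, 0.5 and 0.7. But the plan does not commit to that adjustment, so the unadjusted figures describe the plan as written. They show sensitivity to an unstated quantity, not a shortfall.

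A lost superscript, with 6² printed as 6, is also conceivable. It would lead to the same SD of 6 and the same correction.

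**Conclusion.** The point holds and should be fixed. No reading of 6 as a variance gives 83% power with 25 per arm; the literal readings give 99.9% or more. The figure was very likely an SD of 6, which gives 82.3% to 83.8%, although the cited source could not be checked. Whether it is the SD at one visit or of the 6-month change cannot be settled from the protocol. In the second case the stated power is sound. In the first it holds only for a correlation of about 0.5; it is lower below that and higher above.

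These results assume a true difference of 5, a two-sided alpha of 0.05, equal SDs in both arms and a measured 6-month slope for all 50 patients. They do not show that 25 per arm is too few.

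**What to change.** Check reference 31 and replace the variance of 6 with the confirmed quantity, saying whether it is an SD and of what. State the test and that alpha is two-sided. Then:

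- **If 6 is the SD of the change**, keep 25 per arm and write, for example: *We assume a between-group difference of −5 in the 6-month change in VE/VCO₂ slope and an SD of 6 for that change. With 25 patients per arm, a 6-month slope for all 50, and two-sided alpha 0.05, power is about 82–84% (82% by two-sample t-test).*
- **If 6 is the SD at one visit**, state the correlation assumed between the baseline and final slope, with its source, and restate the power for the change.

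The cost is a source check and a few sentences, with no added patients. In the second case a correlation has to be found and justified. If it is below about 0.5, the power is below 83% and the lower figure has to be reported.

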in ambulatory heart failure patients compared to placebo(18). Furthermore, a meta-analysis of over 34,000 patients in nine cohort studies showed that in terms of overall safety, no increased risk was detected in metformin patients compared to other diabetic agents and, as before, a lower rate of morbidity and mortality was detected among those patients taking metformin(19). A prospective randomized control trial on metformin in heart failure patients with diabetes had to be abandoned because the trialists were unable to find enough patients who met their eligibility criteria due to common use of metformin in the diabetic heart failure population(20). No increased risk of lactic acidosis has been detected clinically and the FDA removed its warning on the use of metformin in stable CHF in 2006.

In the GIPS-III trial, metformin was studied in non-diabetic patients after ST elevation myocardial infarction(21). In this prospective trial of 380 patients with ST elevation MI, metformin was studied for four months at a dose of 500mg twice a day. There was no change in the primary endpoint of left ventricular ejection fraction as measured by CMR, though both groups displayed near normal ejection fractions after four months (53.1% for the metformin group and 54.8% for the placebo group). Though the dose and effect size may have been underpowered for this trial, it did demonstrate outstanding safety profile in cardiovascular patients. There was no reported hypoglycemia or lactic acidosis. Similar safety had been previously seen in pre-diabetic patients, in which a prospective trial of over 3000 patients, randomized to either physical activity, metformin or both, also showed no incidences of hypoglycemia(22).

There have been 11 observational studies published on metformin and heart failure outcomes. In multiple cohorts, metformin use has been associated with decreased mortality, decreased cardiovascular mortality and decreased readmissions(19, 23). In a small randomized pilot of 58 insulin resistant patients with heart failure, metformin use was associated with a decrease in the VE/VCO₂ slope by 4.5

Study Design:

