Prospective, single-center, double-blind, randomized placebo controlled trial of 6 months duration, conducted in a tertiary hospital. Patients will be recruited from the General Cardiology Clinics and Center for Advanced Cardiac Care at New York Presbyterian-Columbia Medical Center. This is an extremely busy outpatient heart failure program in which over 2,500 patients are seen yearly. We propose to enroll n=50 patients.

Study Participants: 50 male and female patients will be recruited.

Inclusion Criteria:

- Age >18yrs old
- Patients with chronic heart failure (defined as >6 months duration) uptitrated to recommended or maximally tolerated dose of ACE-I/ARB (unless contraindicated) and beta-blocker (unless contraindicated). If indicated, an aldosterone receptor antagonist should be given (unless contraindicated).

contraindicated). An ICD and/or CRT should be implanted, if indicated. Patients with a CRT device should be treated for > 3 months.

- Reduced ejection fraction defined as LVEF \leq 35%
- NYHA-class II or III with stable symptoms for at least the past 3 months
- Renal Function by eGFR \geq 45 ml/min (MDRD equation) in accordance with FDA guidance on metformin use in CKD(24)
- Non-insulin resistant defined as a fasting insulin resistance index, or HOMA-IR of <2.7.
- Non-diabetic defined as a HgbA1c <6.0

Exclusion Criteria

- Any oral or injectable hypoglycemic therapy (e.g. insulin, sulfonylureas)
- Known allergy to metformin or major side effects to metformin treatment
- Concomitant use of a carbonic anhydrase inhibitor (such as acetazolamide or topiramate)
- Heart Failure Hospitalizations in the past 3 months (primary diagnosis on admission is heart failure)
- Acute myocardial infarction, unstable angina or revascularization with prior 3 months at the time of randomization
- Planned coronary revascularization, heart surgery, CRT implantation or other intervention during the study period that would potentially affect the function of the heart
- Significant, uncorrected primary cardiac valve disease, specifically severely stenotic or regurgitant mitral or aortic valves
- Cardiac arrest or life threatening ventricular arrhythmias within the last 3 months (unless treated with an ICD)
- Atrial fibrillation with poorly controlled ventricular rate at rest (> 110 beats/min)
- Hypertrophic or restrictive cardiomyopathy, infiltrative or storage myocardial disease, active myocarditis, or pericardial disease.

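### The 83% power follows only if the printed variance of 6 is a standard deviation; the planned effect of -5 is also not reconciled with the 4.5 reported in the Background, and n has no allowance for loss

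*Combined protocol and SAP*

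**What the plan says.** The sample size paragraph (Power for VE/VCO₂) takes its figures from reference 31: "We base the sample size calculation on data from" that source. It continues: "We estimate the average effect size of metformin on the slope of VE/VCO₂ to be -5 with a starting average slope of 32", and gives the variability as "with a starting average slope of 32 and a variance of 6". It concludes: "In order to achieve 83% power with an alpha of 0.05, we will enroll 25 patients in each arm". Sidedness is not stated.

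Three other places bear on this:

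- **Background**, last paragraph before Study Design, on an earlier study: "small randomized pilot of 58 insulin resistant patients with heart failure, metformin use was associated with a decrease in the VE/VCO₂ slope by 4.5". No standard deviation, confidence interval, control-arm change or citation accompanies the figure.
- **Inclusion Criteria**: "Non-insulin resistant defined as a fasting insulin resistance index, or HOMA-IR of <2.7".
- **Statistical Approach**: every randomised patient is analysed. Where the final outcome is missing, the plan uses last observation carried forward (LOCF) as the "approach to assign a final outcome value". Very little loss is expected, and no rate is given. The CPET section and Table 1 place the exercise test at baseline and the final visit only.

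**The concern.** The power paragraph is the only justification for 50 patients, and a reader who puts its printed inputs into a standard formula does not get its printed power. That alone needs correcting.

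Two further features make the 83% look favourable. The planning effect exceeds the one VE/VCO₂ result that the Background describes, and that result came from patients whom the HOMA-IR criterion keeps out of this trial. The calculation also treats all 50 patients as having a measured outcome. Because the only CPET before the final visit is the baseline one, LOCF gives a lost patient a change of exactly zero, and zeros in both arms pull the group difference toward zero.

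At stake is how a null result would be read. A trial described as having 83% power invites more confidence in a negative finding than one whose power may be nearer 74%, or lower if the effect is weaker in patients without insulin resistance.

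**Working it through.** **Inputs.** From the power paragraph: effect 5 (absolute value), variability 6, alpha 0.05, n = 25 per arm. From the Background: 4.5. Two-sided testing is assumed.

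**Formula.** For a two-sample comparison of means, SE = SD × √(2/n), and √(2/25) = 0.2828. By normal approximation, power = Φ(effect/SE − 1.96). The t-test figure uses the noncentral t distribution with 48 degrees of freedom and noncentrality effect/SE.

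**Step 1: the plan's figure, inputs as printed.** Variance 6 gives SD = √6 = 2.449 and SE = 2.449 × 0.2828 = 0.693. Then 5/0.693 = 7.22, and Φ(7.22 − 1.96) = Φ(5.26), which is above 99.9%. The t-test also gives above 99.9%. The printed 83% does not follow.

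**Step 2: the plan's figure, with 6 as an SD.** SE = 6 × 0.2828 = 1.697 and 5/1.697 = 2.946. Φ(0.986) = 83.8%; the t-test gives 82.3%. This reproduces 83%. A one-sided alpha of 0.05 would give 89.6% to 90.3%, so the calculation was evidently two-sided with 6 as an SD.

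**Step 3: smaller effects, complete follow-up, SD of change 6.**

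| Effect | Effect/SE | Normal approximation | t-test |
|---|---|---|---|
| 5 | 2.946 | 83.8% | 82.3% |
| 4.5 | 2.652 | 75.5% | 73.8% |
| 4 (assumed) | 2.357 | 65.4% | 63.7% |

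**Step 4: which SD is it?** The text places the 6 next to the starting slope of 32, so it may describe spread at a single visit. In that case SD of change = 6 × √(2(1 − r)), where r is the baseline-to-final correlation. The documents do not give r; the values below are assumptions.

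| r | SD of change | Power at 5 (t-test) | Power at 4.5 (t-test) |
|---|---|---|---|
| 0.3 | 7.10 | 68% | 59% |
| 0.5 | 6.00 | 82% | 74% |
| 0.7 | 4.65 | 96% | 92% |

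So 74% at 4.5 holds if 6 is the SD of change, or if it is a single-visit SD and r is 0.5.

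**Step 5: loss with LOCF.** Simulated trials had SD of change 6, no mean change in controls, the same random loss probability in both arms, and each lost patient's change set to 0. The loss rates are assumptions.

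| Loss | Power at 5 | Power at 4.5 |
|---|---|---|
| 10% | 77% | 68% |
| 20% | 71% | 62% |

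The results depend on the control arm: if controls change by −2 on average, 20% loss gives 68% and 59%. A cruder calculation that shrinks the effect by the loss fraction but holds the SD at 6 gives 73.8% and 64.8% at 10% loss. Each method gives lower power than complete follow-up.

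**The case against.** The strongest reply is that 83% is not a miscalculation. It reproduces at an effect of 5 with SD 6, so the error is one word, and choosing 5 rather than 4.5 is a design judgement. That stands: the 83% itself should not be called wrong.

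A reader might go further and infer that the trial's true power is 74%, or that the protocol's own evidence contradicts its planning effect. The documents do not support either. The power paragraph cites reference 31, whose data are not shown and which may support -5. The 4.5 carries no citation, comes from an earlier study rather than this trial, and is not shown to be a between-arm difference. What can be said is that two figures stand side by side unreconciled, with no reason given for using the larger. The 74% also depends on which SD the 6 is, as Step 4 shows.

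On loss, the plan expects very little and gives a reason: these patients receive regular care at the centre. The 10% and 20% rates are the review's assumptions, so no particular loss-adjusted power can be attributed to the plan. It remains true that n was not increased for loss and that LOCF here means zero change.

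Nor do the documents show that the effect is smaller without insulin resistance. They show only that carrying it over is not justified or acknowledged.

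**Conclusion.** The point holds in conditional form. As printed, the power statement is wrong: a variance of 6 gives over 99.9%, and 83% requires 6 to be a standard deviation with a two-sided test. That rests on arithmetic alone.

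The planned effect exceeds the only earlier VE/VCO₂ result that the Background describes, and that result is from an excluded population. If 6 is the SD of change and follow-up is complete, power falls from 82% at 5 to 74% at 4.5, about 8 percentage points. If 6 is a single-visit SD, power at 4.5 runs from 59% to 92% for assumed correlations of 0.3 to 0.7. An assumed 10% random loss under LOCF, with no mean change in controls, takes off about 5 to 6 points more.

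None of this shows that 50 patients is the wrong number. It shows that the stated justification cannot be reproduced as written and leaves out the conditions it depends on.

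**What to change.** Keep n = 50 and revise the power paragraph:

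1. Replace variance with standard deviation, and state that the test is two-sided.
2. Have the sponsor confirm whether 6 is the SD of change or of a single measurement. If the latter, state the assumed correlation and recompute.
3. Reconcile -5 with the 4.5 in the Background: cite the source of each, say whether each is a between-arm difference, and give the reason for planning on 5.
4. State power conditionally, for example: *If the SD of change is 6, 25 patients per arm with complete follow-up give 82% power for a difference of 5, 74% for 4.5 and 64% for 4 (two-sided t-test, alpha 0.05).*
5. Note that the pilot effect was seen in insulin-resistant patients and may not hold in this population.
6. If loss is shown, label it as an assumption and give each effect separately: with 10% random loss in both arms, LOCF and no mean change in controls, about 77% at 5 and about 68% at 4.5.

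The change is to text only; no procedure or analysis is altered. The downside is that the stated power becomes less favourable.
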